4.6.4. Additional Safety Analyses

The following additional safety analysis will be provided on Safety-Modified analysis set:

- Overview of all adverse events (including sites 250085 & 250523)
- Summary of on-treatment serious adverse events and adverse events of special interest: incidence, relative risk and risk difference (including sites 250085 & 250523)
- Listing of all adverse events from sites 250085 & 250523

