9.3. Analysis Sets

For the purpose of analyses, the following populations are defined:

Population	Description
Screened	All participants who sign the ICF.
Enrolled	All participants who entered the study. Note screening failures (who never passed screening even if rescreened) and participants screened but never enrolled into the study (Met eligibility but not needed) are excluded from the Enrolled analysis set as they did not enter the study.

Randomised	All participants who were randomly assigned to study intervention in the study.
Full Analysis Set (FAS)	All randomised participants who receive at least one dose of study intervention. Participants will be analysed according to the intervention they are allocated at randomisation. This population will serve as the primary population for analyses of efficacy endpoints.
Safety	All randomised participants who receive at least one dose of study intervention. Participants will be analysed according to the intervention they are allocated at randomisation, unless a participant receives a different intervention to the randomised intervention at all protocol-defined administrations, in which case the participant will be analysed according to the actual intervention they received. This population will serve as the primary population for analyses of safety endpoints.

Further populations to be used for other assessments will be defined in the statistical analysis plan (SAP).

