3. ANALYSIS SETS

Analysis Set	Definition / Criteria	Analyses Evaluated
Screened	All participants who sign the ICF (not including subjects who	 Study Population
	failed at pre-screening).	
Enrolled	All participants who entered the study. Note screening failures (who never passed screening even if rescreened) and participants screened but never enrolled into the study (Met eligibility but not needed) are excluded from the Enrolled analysis set as they did not enter the study.	 Study Population
Randomised	All participants who were randomly assigned to study	 Study Population

Analysis Set	Definition / Criteria	Α	nalyses Evaluated
	intervention in the study.		
Full Analysis Set (FAS)	All randomised participants who receive at least one dose of study intervention excluding participants from sites 250085 & 250523. Data will be analysed according to randomised treatment arm.	• • • •	Study Population Efficacy Immunogenicity PD
FAS-PROMIS	All participants in the FAS population for whom at least one PROMIS fatigue items were administered	•	Health Resource Use Efficacy (PROMIS)
FAS- ADSD/ANSD	All participants in the FAS population for whom at least one ADSD/ANSD questionnaire were administered	•	Efficacy (ADSD/ANSD)
FAS-Japan	All participants in the FAS population who are enrolled from Japan and with Japanese heritage only	•	Study Population Efficacy PD
FAS-Non-Japan	All participants in the FAS population who are not in FAS-Japan analysis set	•	PD
Safety	All randomised participants who receive at least one dose of study intervention excluding participants from sites 250085 & 250523. Participants will be analysed according to the intervention they are allocated at randomisation, unless a participant receives a different intervention to the randomised intervention at all protocol-defined administrations at which study medication was received, in which case the participant will be analysed according to the actual intervention they received. This population will serve as the primary population for analyses of safety endpoints.	•	Safety
Safety-Japan	All participants in the Safety population who are enrolled from Japan and with Japanese heritage only	•	Safety
Safety-Non- Japan	All participants in the Safety population who are not in Safety- Japan analysis set	•	Not planned in this SAP but flagged for future analysis
PK	All participants in the FAS population for whom at least one pharmacokinetic sample was obtained, analysed and was measurable.	•	PK

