PK-Japan	All participants in the PK population who are enrolled from Japan and with Japanese heritage only	•	РК
PK-Non-Japan	All participants in the PK population who are not in PK- Japan analysis set	•	РК
FAS-Modified	All participants in the FAS population plus randomised particiants from sites 250085 & 250523 who receive at least one dose of study intervention.	•	Efficacy (Primary and Secondary)
Safety-Modified	All participants in the Safety population plus randomised particiants from sites 250085 & 250523 who received at least one dose of study intervention. Participants will be analysed according to the intervention they are allocated at randomisation, unless a participant receives a different intervention to the randomised intervention at all protocol- defined administrations at which study medication was received, in which case the participant will be analysed according to the actual intervention they received.	•	Key Safety
FAS- ADSD/ANSD- Modified	All participants in the FAS-ADSD/ANSD population plus randomised participants from sites 250085 & 250523 who receive at least one dose of study intervention.	•	Efficacy (ADSD/ANSD)

Note: GCP non-compliance/significant data integrity concern at Sites 250085 & 250523 was identified.

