4.6. Safety Analyses

All safety analyses will be performed on the Safety Analysis Set unless otherwise specified. Summaries of data will report data according to the nominal visit for which it was recorded. Occurrence of Adverse Events (AEs), Serious Adverse Events (SAEs), Adverse Events of Special Interest (AESIs), laboratory data, vital signs, and ECGs will be included in data displays in the form of frequency tables, summary statistics, graphs, and statistical analyses where appropriate.

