4.6.2.1. Adverse Events of Special Interest

Adverse events of special interest (AESI) for GSK3511294 program include:

• Allergic (Type 1 hypersensitivity) reactions including anaphylaxis

Note: these events will be assessed by the investigator as to whether they meet the diagnostic criteria for anaphylaxis as outlined by the 2006 Joint NIAID/FAAN Second Symposium on Anaphylaxis.

- Type III hypersensitivity (immune complex disease/vasculitis) reactions
- Local injection site reactions
- QTc prolongation

AESI reported by the investigator as systemic reactions (further categorised by the investigator as either allergic [type I hypersensitivity] or other systemic reactions and assessed against Sampson criteria for anaphylaxis) are collected via targeted eCRF within the study. Vasculitis events and local injection site reactions are also collected via targeted eCRF within the study.

Separate summary tables showing the number and percent of subjects with each type of AESI (excluding QTc prolongation) broken down by preferred term will be created.

For each type of AESI (excluding QTc prolongation) a profile summary table will be produced containing information including, but not limited to, the number of occurrences of the event, event characteristics, time to onset, intensity, outcome and action taken.

A summary of the incidence of serious adverse events and adverse events of special interest (excluding QTc prolongation) will be produced displaying the relative risk and risk difference and their 95% CIs between and GSK3511294 and placebo.

AESI of QTc prolongation will be summarised as detailed in Section 4.6.3.3 ECG.

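### ECG, laboratory and liver findings in dosed participants at two excluded sites appear in no SAP-specified output unless they were recorded as AEs or SAEs

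*SAP*

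**What the plan says.** Protocol 9.3 defines the Safety population as "All randomised participants who receive at least one dose of study intervention", with no site exclusion, and adds: "This population will serve as the primary population for analyses of safety endpoints". Protocol 9.4.5 assigns all safety analyses to that population.

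SAP section 3 defines its Safety set as "All randomised participants who receive at least one dose of study intervention excluding participants from sites 250085 & 250523". The note under the table gives the reason: "GCP non-compliance/significant data integrity concern at Sites 250085 & 250523 was identified". The same section creates Safety-Modified, "All participants in the Safety population plus randomised particiants from sites 250085 & 250523 who received at least one dose of study intervention", and earmarks it for key safety.

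SAP 4.6 sets the default: "All safety analyses will be performed on the Safety Analysis Set unless otherwise specified". Sections 4.6.3.1 (laboratory and liver) and 4.6.3.3 (ECG) name no other set.

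SAP 4.6.4 opens with "The following additional safety analysis will be provided on Safety-Modified analysis set" and gives three items: an AE overview, a table of on-treatment SAEs and AESIs with relative risk and risk difference, and a listing of AEs at the two sites.

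The corresponding SAE/AESI table on the Safety set, in SAP 4.6.2.1, reads: "A summary of the incidence of serious adverse events and adverse events of special interest (excluding QTc prolongation) will be produced". That section sends QTc prolongation to the ECG section instead.

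**The concern.** Leaving out sites with a serious integrity problem is a reasonable choice for the main analyses. For safety, though, the reader also needs to see everyone who received the drug, and the protocol promised that. The SAP meets this need only for events that a site chose to record as AEs. The measured data from the same participants (QTcF and QT values, ALT and bilirubin, liver stopping or monitoring events) have no add-back.

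QTc prolongation is one of four AESIs in Protocol 8.4.7, and Protocol 2.3.1 describes a QTc finding in monkeys at the high dose. Liver chemistry has its own stopping rules in Protocol 7.1.1 and Appendix 6. If a participant at one of the two sites met a QT or liver stopping criterion and it was not entered as an AE, the outputs the SAP specifies would not show it.

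**Working it through.** There is no stated figure to reproduce. The check is to follow a dosed participant at one of the two sites through each safety output.

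1. **Membership.** Under Protocol 9.3 the participant is in the Safety population. Under SAP section 3 the participant is out of the Safety set and in Safety-Modified.
2. **Default.** Under SAP 4.6, any safety output that does not name another set uses the Safety set, so the participant is out.
3. **Output by output.**

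| Output | SAP section | Set that applies | Participant included? |
|---|---|---|---|
| AE overview, repeated | 4.6.4 | Safety-Modified | Yes |
| SAE/AESI relative-risk table, repeated | 4.6.4 | Safety-Modified | Yes, but QTc coverage unclear |
| AE listing for the two sites | 4.6.4 | Safety-Modified | Yes |
| QTcF and QT category tables | 4.6.3.3 | Safety (default) | No |
| ECG listing for QT stopping criteria | 4.6.3.3 | Safety (default) | No |
| Maximum ALT against maximum bilirubin plot | 4.6.3.1 | Safety (default) | No |
| Liver stopping/monitoring summaries | 4.6.3.1 | Safety (default) | No |

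4. **QTc in the repeated AESI table.** SAP 4.6.2.1 leaves QTc prolongation out of its version of the table. The item in 4.6.4 has no such exclusion. Both readings are possible. Even if QTc is included, the table counts reported events, not QTcF values.
5. **Does the AE route catch the rest?** Only in part.
   - Protocol 8.3.4 and Appendix 3 (10.3.1) make a laboratory or ECG abnormality an AE when the investigator judges it clinically significant.
   - Possible Hy's Law cases must be reported as SAEs (Protocol 10.3.2), so they do reach the repeated outputs.
   - Appendix 6 treats ALT of at least 8 times ULN as a stopping criterion by itself. It asks for a liver event form, and for an SAE form only if the event also meets SAE criteria.
   - A stopping-level value can therefore exist without an AE record, depending on a judgement made at a site under an integrity concern.

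The efficacy side is handled more fully. SAP 4.2.2 and 4.3.2 repeat the primary and main secondary analyses on FAS-Modified, and 4.4.10.1 repeats ADSD/ANSD on its own modified set. SAP 4.12, on changes from the protocol, does not mention the altered Safety set. The version history for Amendment 02 does.

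**The case against.** The limited add-back is deliberate and disclosed. The version history says the sites were removed for the main analyses, and the modified set is earmarked for key safety. Repeating AE, SAE and AESI outputs but not every numeric display from doubtful sites is defensible, and most findings of clinical consequence should become AEs or SAEs. This supports keeping the main analysis as it is and not repeating everything. It does not explain why the QT-stopping listing and the liver stopping/monitoring summaries, which are short and central to safety, leave out exposed participants.

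A reader might infer three stronger points that the documents do not support.

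- **That these findings are seen nowhere.** SAP section 1 and 4.6.3.1 defer display details to the Output and Programming Specification, which was not available. SAP 4.11.1 has the IDMC reviewing laboratory and ECG data separately. The supportable statement is limited to outputs the SAP specifies.
- **That QTc prolongation is definitely excluded from the all-dosed AESI table.** That is inferred from 4.6.2.1. Section 4.6.4 does not say it, and the AE listing there would show any QTc event recorded as an AE.
- **That the omitted data are immune to the site problem because they are read centrally.** Protocol 7.1.2 uses machine reads at Visit 10 for stopping, Appendix 2 allows local laboratory results in some circumstances, and the sites still acquire the tracings and samples. The SAP does not describe the integrity concern, so its reach into these data is unknown.

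**Conclusion.** The point holds as a reporting gap. Followed as written, the SAP gives no ECG, laboratory or liver display covering everyone dosed. Findings of these kinds at the two sites are specified for display only if recorded as AEs or SAEs. Whether QTc prolongation counts in the Safety-Modified AESI table is ambiguous and should be settled.

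No magnitude is claimed. The documents give neither the number dosed at the two sites nor any event rate there, so it cannot be said that the safety conclusion would change. The point is minor: it leaves the primary efficacy conclusion and the main safety analysis untouched. It assumes that the default in SAP 4.6 applies wherever no other set is named, and that the Output and Programming Specification does not already add these displays.

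**What to change.** In SAP 4.6.4, add on Safety-Modified:

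- the QTcF and QT category tables and the listing for participants meeting QT stopping criteria, from 4.6.3.3;
- the ALT against bilirubin plot and the liver stopping/monitoring event summary, from 4.6.3.1.

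At minimum, list these data for the two sites. In either case, footnote the data-integrity concern. State whether the Safety-Modified AESI table includes QTc prolongation. If the Output and Programming Specification already provides these displays, a cross-reference in 4.6.4 is enough.

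The cost is a few extra outputs from existing programs on a set already defined. The downside is showing data from sites under an integrity concern, which the footnote addresses. The main analysis does not change.

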4.7. Immunogenicity Analyses

For the immunogenicity assessment, two types of anti-drug antibody (ADA) assays will be performed, a binding antibody assay and a neutralizing antibody assay (NAb).

For the binding assay, there will be a three-tiered analysis: screening, confirmation and titration. The screening assay produces a result of positive or negative relative to a screening cut point. Positive samples continue with the confirmation assay, which also produces a result of positive or negative relative to a confirmation cut point. For positive confirmation samples, a titre value will also be obtained to quantify the degree of binding in a titration assay, and the sample will be tested with the neutralizing assay, which also reports results as positive or negative. A sample that is positive in the confirmation assay is considered positive for anti-GSK3511294 antibodies.

All participants' baseline immunogenicity samples will be analysed. Post-baseline immunogenicity samples will only be analysed for participants receiving GSK3511294 100 mg SC.

The following descriptive summaries will be presented for GSK3511294 100 mg SC group by visit using FAS population.:

- Summary of binding antibody assay results: it will summarise the binding antibody confirmatory assay results at each visit. Summary will include categories for negative and positive results, sub categories for transient positive and persistent positive (see note below), and available titre values (min, median and max). It will also summarise the highest post-baseline binding antibody confirmatory assay result obtained.
- Summary of binding antibody results for participants without positive result prior to dosing: it will summarise the binding antibody confirmatory assay results at each visit. Summary will include categories for negative and positive results, sub categories for transient positive and persistent positive (see note below), and available titre values (min, median and max). It will also summarise the highest post-baseline binding antibody confirmatory assay result obtained.
- Summary of neutralizing antibody assay results: it will summarise the neutralising antibody assay results for participants with a positive binding antibody confirmatory assay results. Neutralising antibody assay results will be categorised as positive or negative. It will also summarise the highest post-baseline neutralizing antibody assay result obtained.
- Summary of AE by highest post-baseline binding antibody confirmatory assay result

The following descriptive summaries will be presented for the placebo group using FAS population:

- Summary of binding antibody assay results for all baseline visit results. Summary will include categories for negative and positive results, and available titre value (min, median and max).
- Summary of neutralizing antibody assay results for all baseline visit results. Summary will include categories for negative and positive results.

Note: Visits will include pre-dose baseline visit and all post-baseline visits where immunogenicity assessments were performed. The binding antibody confirmatory assay results are categorised as negative or positive. The positive results will have two sub categories: transient positive (defined as a single confirmatory positive immunogenic response that does not occur at the final study assessment) or persistent positive (defined as a confirmatory positive immunogenic response for at least 2 consecutive assessments or a single result at the final study assessment). For the summary of highest postbaseline binding antibody confirmatory assay result and neutralizing antibody assay result, subjects with both positive and negative results will be identified in the positive category. If a subject had titre results that fall into multiple titre result categories, they will be included in the highest category.

4.8. Healthcare Resource Utilization

The total number of visits per participant for each type of healthcare contact: non inpatient (home visits [day], home visits [night], physician office/clinic visits, urgent care/outpatient clinic visits, emergency room visits, telephone calls, telemedicine

consultations) and inpatient admissions (intensive care unit and general hospital wards) will be presented by summarising the respective visits and number of days (Length of Stay-LOS). This will also be summarised for each contact type (asthma-exacerbations, other healthcare contact).

4.9. Risk Benefit Analyses

A forest plot will be produced to display efficacy and safety data from analyses in adjacent panels using Full Analysis Set.

The efficacy results will include primary endpoint (and its associated endpoint), i.e. clinically significant exacerbations (and exacerbations requiring hospitalisation and/or ED visit). The AE results will be obtained from the analyses as described in Section 4.6.2.1 for the following categories of AEs:

- On-treatment SAE
- Systemic Reactions
 - Allergic (Type 1 hypersensitivity) reactions
 - Anaphylaxis
 - Other systemic reactions
- Type III hypersensitivity/vasculitis
- Local injection site reactions

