8.2.2. Asthma Exacerbations

Clinically significant exacerbations of asthma are defined by:

Worsening of asthma which requires use of systemic CSs¹ and/or hospitalisation and/or Emergency Department (ED) visit.

¹For all participants, IV or oral steroids (e.g., prednisone) for at least 3 days or a single IM CS dose is required. For participants on maintenance systemic CSs, at least double the existing maintenance dose for at least 3 days is required.

Exacerbations separated by less than 7 days will be treated as a continuation of the same exacerbation.

Details of each asthma exacerbation, including medications used to treat exacerbations should be recorded in the eCRF.

Asthma exacerbations should not be recorded as an AE unless they meet the definition of a SAE.

The time period for collection of exacerbation information in the eCRF will be from the start of study intervention until the Exit Visit or Follow-up Visit if applicable.

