8.4. Adverse Events (AEs), Serious Adverse Events (SAEs) and Other Safety Reporting

The definitions of adverse events (AE) or serious adverse events (SAEs) can be found in Section 10.3. Asthma exacerbations should not be recorded in the AE section of the eCRF unless they meet the definition of a SAE.

The definitions of device-related safety events, (adverse device effects [ADEs] and serious adverse device effects [SADEs]), can be found in Section 10.7. Device deficiencies are covered in Section 10.7.

AEs will be reported by the participant (or, when appropriate, by a caregiver, surrogate, or the participant's legally authorised representative).

The investigator and any qualified designees are responsible for detecting, documenting, and reporting events that meet the definition of an AE or SAE and remain responsible for following up all AEs that are serious, considered related to the study intervention or the study, or that caused the participant to discontinue the study (see Section 7).

The method of recording, evaluating, and assessing causality of AEs and SAEs and the procedures for completing and transmitting SAE reports are provided in Section 10.3.

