10.3.1. Definition of AE

AE Definition

 An AE is any untoward medical occurrence in a clinical study participant, temporally associated with the use of a study intervention, whether or not considered related to the study intervention. 
NOTE: An AE can therefore be any unfavourable and unintended sign (including an abnormal laboratory finding), symptom, or disease (new or exacerbated) temporally associated with the use of a study intervention.

Events Meeting the AE Definition

 Any abnormal laboratory test results (haematology, clinical chemistry, or urinalysis) or other safety assessments (e.g., ECG, radiological scans, vital signs measurements), including those that worsen from baseline, considered clinically significant in the medical and scientific judgment of the investigator (i.e., not related to progression of underlying disease). Exacerbation of a chronic or intermittent pre-existing condition including either an increase in frequency and/or intensity of the condition. New conditions detected or diagnosed after study intervention administration even though it may have been present before the start of the study. Signs, symptoms, or the clinical sequelae of a suspected intervention- intervention interaction. Signs, symptoms, or the clinical sequelae of a suspected overdose of either study intervention or a concomitant medication. Overdose per se will not be reported as an AE/SAE unless it is an intentional overdose taken with possible suicidal/self-harming intent. Such overdoses should be reported regardless of sequelae. "Lack of efficacy" or "failure of expected pharmacological action" per se will not be reported as an AE or SAE. Such instances will be captured in the efficacy assessments. However, the signs, symptoms, and/or clinical sequelae resulting from lack of efficacy will be reported as AE or SAE if they fulfil the definition of an AE or SAE.

Events NOT Meeting the AE Definition

- Any clinically significant abnormal laboratory findings or other abnormal safety assessments which are associated with the underlying disease, unless judged by the investigator to be more severe than expected for the participant's condition.
- The disease/disorder being studied or expected progression, signs, or symptoms of the disease/disorder being studied, unless more severe than expected for the participant's condition.

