10.3.2. Definition of SAE

If an event is not an AE per definition above, then it cannot be an SAE even if serious conditions are met (e.g., hospitalisation for signs/symptoms of the disease under study, death due to progression of disease, etc.).

An SAE is defined as any untoward medical occurrence that, at any dose, meets one or more of the criteria listed:

a. Results in death**b. Is life-threatening**

The term 'life-threatening' in the definition of 'serious' refers to an event in which the participant was at risk of death at the time of the event. It does not refer to an event, which hypothetically might have caused death, if it were more severe.

c. Requires inpatient hospitalisation or prolongation of existing hospitalisation

- In general, hospitalisation signifies that the participant has been admitted (usually involving at least an overnight stay) at the hospital or emergency ward for observation and/or treatment that would not have been appropriate in the physician's office or outpatient setting. Complications that occur during hospitalisation are AE. If a complication prolongs hospitalisation or fulfils any other serious criteria, the event is serious. When in doubt as to whether "hospitalisation" occurred or was necessary, the AE should be considered serious.
- Hospitalisation for elective treatment of a pre-existing condition that did not worsen from baseline is not considered an AE.

d. Results in persistent or significant disability/incapacity
 
 • The term disability means a substantial disruption of a person’s ability to conduct normal life functions. • This definition is not intended to include experiences of relatively minor medical significance such as uncomplicated headache, nausea, vomiting, diarrhoea, influenza, and accidental trauma (e.g. sprained ankle) which may interfere with or prevent everyday life functions but do not constitute a substantial disruption.

e. Is a congenital anomaly/birth defect

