5.1.1. Primary Endpoint

The assumed true annualised rate of exacerbations in the placebo arm is 1.18. Based on an assumed true treatment difference of a 50% reduction in annualised exacerbation rate between GSK3511294 + SoC and placebo + SoC, a sample size of 375 randomised participants (250 to GSK3511294, 125 to placebo) will provide 99% power for the primary endpoint at a 5% two-sided significance level [PASS, 2020].

The assumptions for the placebo rate and treatment effect are median values from an elicitation exercise which used Phase 3 anti-IL-5/5R historical data (~50% reduction in exacerbations) and expert opinion. The sample size is based also on an assumption of 0.8 for the dispersion parameter which was observed in two mepolizumab studies [Pavord, 2012; Ortega, 2014]. It was assumed that 14% of participant-years data will be missing due to study withdrawal, which is also consistent with mepolizumab studies.

Based on the assumptions above, the minimum observed treatment difference estimated to result in significance at the 5% two-sided significance level is a 27% reduction in exacerbations for GSK3511294 + SoC compared with placebo + SoC (rate ratio of 0.73).

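### The all-SAE row in the benefit-risk plot includes any asthma exacerbation recorded as an SAE, so efficacy pulls that row towards benefit; a row without asthma exacerbations should stand beside it

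*SAP*

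**What the plan says.** SAP 4.9 plans one forest plot with adjacent panels. The efficacy panel shows clinically significant exacerbations and those requiring hospitalisation or an ED visit. The safety panel lists on-treatment SAEs, systemic reactions (allergic, anaphylaxis, other), type III hypersensitivity/vasculitis and local injection site reactions. On the source of the safety rows it says: "The AE results will be obtained from the analyses as described in Section 4.6.2.1 for the following categories of AEs".

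That source, SAP 4.6.2.1, says: "A summary of the incidence of serious adverse events and adverse events of special interest (excluding QTc prolongation) will be produced displaying the relative risk", with risk difference and 95% CIs. The only exclusion named is QTc prolongation. SAP 4.6.4 repeats the summary on the Safety-Modified set.

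On whether an exacerbation can be an SAE, the protocol speaks in two places:

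- Section 8.2.2: "Asthma exacerbations should not be recorded as an AE unless they meet the definition of a SAE". Section 8.4 says the same of the AE section of the eCRF. One of the SAE criteria in 10.3.2 is: "Requires inpatient hospitalisation or prolongation of existing hospitalisation".
- Section 10.3.1 lists among events that are not AEs: "The disease/disorder being studied or expected progression, signs, or symptoms of the disease/disorder being studied, unless more severe than expected" for the participant's condition. Section 10.3.2 adds: "If an event is not an AE per definition above, then it cannot be an SAE even if serious conditions are met". Its example is hospitalisation for signs or symptoms of the disease under study.

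Neither document names a pooled SAE contrast without asthma events.

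**The concern.** The SAE row is there to measure harm. An exacerbation recorded as an SAE is also an efficacy event, so each one that the drug prevents improves both panels. The trial is sized on an "assumed true treatment difference of a 50% reduction in annualised exacerbation rate". If serious exacerbations fall in a similar way, the aggregate SAE relative risk drops below 1 with no effect at all on other SAEs. A true excess of other SAEs could then appear as little or no difference in the one display built to weigh benefit against risk. What is at stake is the reading of that row and of the 4.6.2.1 and 4.6.4 summaries behind it. No hypothesis test, decision rule or primary inference uses them.

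**Working it through.** **What the documents supply.** They give no SAE rate, SAE relative risk or safety power, so there is no stated figure to reproduce for this point. The input that sets the direction is the assumed 50% reduction, which belongs to the primary power calculation, and that calculation reproduces. With placebo rate 1.18, drug rate 0.59, dispersion 0.8, mean follow-up 0.86 year (14% of participant-years missing) and 250/125 participants:

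var(log rate ratio) = (1/(0.86×1.18) + 0.8)/125 + (1/(0.86×0.59) + 0.8)/250 = 0.01428 + 0.01108 = 0.02537, so SE = 0.159.

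Power = Φ(0.693/0.159 − 1.96) = 99.2% (stated 99%). The significance boundary is exp(−1.96×0.159) = 0.73, as stated.

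**Size of the pull (assumed SAE risks).** Let n0 and n1 be the placebo and drug risks of a non-asthma SAE, and a0 and a1 = 0.5×a0 the risks of an asthma SAE. Taking the two as independent, the any-SAE risk in an arm is p = 1 − (1 − n)(1 − a). To a close approximation:

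all-SAE risk difference ≈ (n1 − n0) − 0.5×a0.

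A halved asthma-SAE risk therefore offsets a non-asthma excess of about half the placebo asthma-SAE risk. In the drug arm of 250 this is about 1 point (2.5 participants) at a0 = 2%, 2 points (5) at 4% and 3 points (7.5) at 6%.

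| Assumed placebo asthma-SAE risk | All-SAE RR (RD, points) if non-asthma SAEs go from 3% to 6% | All-SAE RR (RD, points) if non-asthma SAEs go from 6% to 9% |
|---|---|---|
| 0% | 2.00 (+3.0) | 1.50 (+3.0) |
| 1% | 1.63 (+2.5) | 1.36 (+2.5) |
| 2% | 1.40 (+2.0) | 1.26 (+2.0) |
| 4% | 1.15 (+1.0) | 1.11 (+1.1) |
| 6% | 1.00 (0.0) | 1.01 (+0.1) |
| 8% | 0.91 (−1.0) | 0.93 (−0.9) |

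Worked cell (3% to 6%, a0 = 6%): placebo 1 − 0.97×0.94 = 8.8%; drug 1 − 0.94×0.97 = 8.8%; RR 1.00.

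With no effect on other SAEs (6% in both arms), the all-SAE RR is 6.94%/7.88% = 0.88 at a0 = 2% and 9.76%/13.52% = 0.72 at a0 = 8%.

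**Precision.** With SE(log RR) = √[(1 − p1)/(250×p1) + (1 − p0)/(125×p0)], the non-asthma contrast of 6% against 3% has RR 2.00 (95% CI 0.66 to 6.08). The all-SAE row in the worked cell has RR 1.00 (0.50 to 1.99). Both intervals are wide.

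**Scale.** SAP 4.3.3 analyses the hospitalisation/ED endpoint only if the study has at least 20 such events. At exactly 20 events, 2:1 allocation and a halved rate, the split is about 10 to 10: 10/125 = 8% on placebo and 10/250 = 4% on drug, at one event per participant. ED-only visits are included and need not be SAEs. Twenty is a threshold, not a forecast, so this only indicates the order of magnitude.

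**The case against.** **The overlap may be small.** A reader might infer that every hospitalised exacerbation is an SAE and so counts twice. The documents do not support that. Protocol 10.3.1 takes the disease under study out of the AE definition unless it is more severe than expected, and 10.3.2 gives hospitalisation for it as an example of a non-SAE. On that text, many asthma admissions might never reach the SAE row. This stands as a limit on size. It does not remove the overlap, because exacerbations more severe than expected still qualify and 8.2.2 and 8.4 plainly foresee exacerbations as SAEs.

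**A harm would be visible elsewhere.** A reader might infer that the plan hides a non-asthma excess from the report. It does not. SAP 4.6.2 tabulates all SAEs by system organ class and preferred term, with separate summaries of related SAEs and fatal SAEs in the overview. The AESI categories have their own relative risks and their own rows in the same panel. The IDMC also reviews unblinded SAEs (SAP 4.11.1). This stands too; what is missing is a pooled non-asthma relative risk and risk difference.

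**An all-cause SAE row is legitimate.** It is a valid net measure, so replacing it is not warranted. Dropping every SAE linked to an exacerbation record could also remove real harms, such as a serious infection or hypersensitivity reaction that triggered an exacerbation.

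**Display detail sits elsewhere.** SAP Section 1 leaves display specifications to the Output and Programming Specification, so an extra row there cannot be ruled out. But 4.9 lists its categories, and this one is not among them.

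**Conclusion.** The point holds as a limitation of one aggregate contrast. The SAE relative risk and risk difference in SAP 4.6.2.1, 4.6.4 and 4.9 include any exacerbation recorded as an SAE, and the same events count in the efficacy panel. If the drug reduces serious exacerbations, that contrast is pulled towards benefit and can dilute or offset an excess of other SAEs in that display.

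The size is unknown. The offset is about half the placebo asthma-SAE risk, assuming that this risk is halved. The plan's 50% refers to the rate of all clinically significant exacerbations, not to a participant's risk of an asthma SAE. The SAE risks used are assumptions, and the offset is zero if no exacerbation is recorded as an SAE. At 250/125 the intervals are wide with or without the change, so the extra row would correct the direction of the estimate but would not by itself establish a harm.

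**What to change.** Keep the all-SAE row in SAP 4.6.2.1, 4.6.4 and 4.9. Beside it, add a pre-specified row for SAEs excluding asthma exacerbations, with relative risk, risk difference and 95% CIs. Exclude only SAEs whose preferred term is asthma or asthma exacerbation, not every SAE linked to an exacerbation record. Add a footnote to the 4.9 plot saying that the all-SAE row overlaps with the efficacy panel.

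Protocol 8.2.2 and 8.4 must also be reconciled with 10.3.1 and 10.3.2, so that sites apply one rule on when an exacerbation is recorded as an SAE.

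The analysis change costs one extra descriptive row from data already collected, plus a list of preferred terms fixed before unblinding. It alters no hypothesis test or alpha allocation.
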